#### **Develop Training Materials**

Research team members will work with OCHIN's training and QI teams, with CHC clinician input, to develop an initial set of resources for implementing CV Wizard in CHC workflows. These materials will be augmented over time, as described below, but at first will include information on how CV Wizard works, how it might be integrated into CHC workflows, and how care team members can use CV Wizard to present/discuss CVD risks with patients in a manner that minimizes patient discomfort, reduces potential adverse effects, and maximizes patient engagement.

## **Implementation** Support

CV Wizard's impact will be affected by the CHCs' ability to implement it and achieve ongoing use at targeted visits. We will provide iterative, adaptive, pragmatic approach to providing the study CHCs with implementation support, as follows:

- (1) When Arm 1 CHCs implement CV Wizard, they will receive the basic implementation support that OCHIN's QI team provides with any new EHR functions (e.g., written materials, a live monthly webinar describing CV Wizard and suggested workflows for its use). We will also provide monthly CV Wizard use-rate reports to the Arm 1 CHC providers and clinic managers. CDS use rates are based on proportion of targeted visits where the CDS is viewed and / or printed.
- (2) For the next 18 months, we will review monthly use rates of CV Wizard in the Arm 1 CHCs. The OCHIN practice facilitator will contact operational leaders at the CHCs with low adoption rates to ask about barriers to uptake, and what might help address these barriers; this aligns with the QI support that OCHIN regularly provides its member CHCs. We will work iteratively with OCHIN's Implementation and Training teams to develop and provide additional support as needed to address identified barriers to adoption and sustained use at the desired level (80% of targeted visits). The specifics of this ongoing support will be determined based on CHC need. However, based on our team's expertise/experience and the implementation science literature, we anticipate that some CHCs may need additional training on integrating CDS tools with clinic workflows; harnessing use rate data to guide subsequent efforts; the evidence-based guidelines underlying the CDS; and how to use CV Wizard to engage patients. Such trainings will be provided to clinic leaders, providers, managers, QI coordinators and administrators at the study CHCs via written materials and monthly webinars. If indicated, we will also provide academic detailing relating to the CDS, and customized implementation plans. These resources will become part of our revised implementation materials. We will also conduct monthly interactive webinars to answer questions, identify additional barriers to uptake/needed training, and enable peer-to-peer learning in the Arm 1 CHCs. If there are CHCs for whom these approaches do not enhance uptake, we will confer with CHC clinicians, OCHIN's QI team, and our team's implementation scientists to identify and implement alternative strategies.
- (3) Arm 2 clinics will receive the revised implementation materials when CV Wizard is activated in their EHR. We will conduct a similar process to attempt to further improve these materials. We will collect quantitative data on which staff members from each

study CHC take part in each training activity, and qualitative data on perceptions of the training strategies.

#### **Data Collection**

The mixed methods process evaluation will explore "what works, for whom and in what circumstances" related to CDS uptake, guided by our logic model and the Technology Acceptance Model (TAM). Our 3-tiered approach to data collection follows recent guidance on process evaluation of complex interventions which advocates complementing collecting key variables from all sites with in-depth data from purposively selected samples. This balances collecting data detailed enough to enable transferability (degree to which results can be applied to other contexts) and pragmatism (what is possible).

(1) All Clinics –We will collect the following information as it pertains to all clinics participating in the study: (1) baseline clinic data (e.g., location, patient characteristics, clinic characteristics, clinic size, etc.); (2) all 'trouble-tickets' relevant to CV Wizard submitted to OCHIN via its member help request system; (3) all user feedback submitted via CV Wizard's feedback mechanism; (4) all exchanges from the implementation support webinars; and (5) feedback from the practice facilitator and others involved with implementation support.

We will also collect attendee evaluations of all webinars. This pragmatic, adaptive approach will let us explore how to help diverse CHCs implement CDS, fine-tune materials and strategies for doing so, identify key barriers to adoption of CDS, and inform developing a guide for CHCs implementing CV Wizard.

SUPPLEMENT ADDENDUM		
Process outcomes	Description	
Encounter patterns	(i) Total clinical encounters; % in-person, by video, or by phone	
	(ii) % of patients whose encounters were all in-person, all VC, or a mix of	
	both	
	(iii) % encounters where CV Wizard alerts that there are CDS suggestions,	
	i.e., identified a target patient	
Missed / delayed	(i) % of scheduled appointments that are missed / cancelled, by encounter	
encounters	type	
	(ii) Appointment wait times (time from scheduling call to appointment), by	
	encounter type	
Tool use	% of encounters where care team member 'used' (viewed) suggested CV	
	Wizard CDS, by encounter type (among encounters occurring after CV	
	Wizard was activated at the clinic)	
Primary outcomes	Description	
CVD risk data up to	(i) % patients with up-to-date BP documented in EHR by 6 months post-	
date	index visit, and (ii) % patients with up-to-date A1c data documented in	
	EHR by 6 months post-index visit, by encounter type	
	Note: These outcomes will be adjusted for # of encounters in follow-up	
	period. Analyses of A1c updates will account for whether prior A1c	
	measure indicated lack of control and need for more frequent monitoring.	
	Note: We will consider using coding of a hypertension diagnosis at index	
	and follow-up encounters as a proxy for updated BP.	
Effectiveness (all	Needed care provided within 7 days of encounter, by encounter type; e.g.,	
eligible patients)	If CV Wizard suggested (or would have suggested, if used) starting a statin,	

	was prescription issued: YN; If an A1c test, was the test ordered: YN; If a
	referral to a nutritionist, was the referral made: YN; If medications to help
	quit smoking, was prescription issued; etc.
Effectiveness (subset	Change in CVD risk over time, measured as:
of patients with an	(i) Decrease in total reversible CVD risk score (ACC/AHA 10-year pooled
index encounter and	ASCVD risk score  )
≥1 encounters ≥6 months post-index)	(ii) Change from BP at index visit to increased, decreased, or no change, by end of follow-up period.
,	(iii) Among patients with uncontrolled A1c (>8%) at index encounter, % in
	control by end of follow-up period; among patients with controlled A1c
	(≤8%) at index, % who had a 'relapse' by end of follow-up.
Potential covariates	Description
Patient	Age; gender; race / ethnicity; poverty; insurance status at index; #
characteristics	encounters to site / provider, prior year
Comorbid conditions	Severe mental illness or diabetes diagnosis at index visit
Index characteristics	New patient to the clinic: YN
	l l
Post-index	# in-person / VC encounters between index visit and end of follow-up
Post-index encounters	

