### **Specific Aims**

**Aim 1.** Conduct a clinic-randomized trial of the impact of an evidence-based point-of-care CDS system on (i) overall CVD risk scores, and (ii) control of individual CVD risk factors (blood pressure; HbA1c, lipid levels; smoking; body mass index), among high CVD risk adult CHC patients.

**Aim 2.** Develop and hone need-based implementation support protocols to help Arm 1 CHCs implement the CV Wizard CDS system into their standard workflows; assess whether use of the protocols developed for Arm 1 CHCs accelerates implementation and adoption of the CDS system in the Arm 2 CHCs. **Supplement Addendum:** Compare CVD risk management in high-risk patients at in-person vs. virtual care (VC) encounters, in the periods pre- and post-COVID's onset.

**Aim 3.** Conduct a mixed methods process evaluation, guided by the Technology Acceptance Model (TAM), to identify and address patient, provider, and delivery system barriers to uptake/impact of this CDS in CHCs. **Supplement Addendum:** In a subset of study clinics, explore how CV Wizard's individualized, prioritized CVD risk summary is used in VC to guide care decisions and engage patients in shared decision-making.

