#### **Supplement Addendum**

- (1) Descriptive Analyses (Aim 2a)
  - We will conduct a descriptive analysis on the following process outcomes: (1) Encounter patterns; (2) Rates of missed or cancelled appointments at in-person vs. VC (telephone, video) encounters; (3) Appointment wait times by encounter type, and (4) CV Wizard use (in encounters where there are CV Wizard CDS suggestions by encounter type.
  - We will use standard statistical tests (e.g., chi-square, t-tests) to describe measures in the periods pre- vs. post-COVID's onset.
- (2) Regression Analyses (Aim 2b)
  - Encounter is the unit of analysis.
  - We will assess associations between encounter type and: (1) Action taken on needed care plan components; (2) Up-to-date documentation of BP and A1c by 6 months postindex visit (accounting for whether BP data were taken in person or reported by the patient); and (3) Change in CVD risk factors by end of follow-up period. To do so, we will conduct adjusted regression analyses using longitudinal electronic health record data.

- To assess action taken on needed care, data for each factor will be extracted at each
  visit in the study period. We will use adjusted logistic regression models, with a
  dichotomous outcome of action taken or not taken.
- To assess *impact on individual CVD risk factors*, data for each factor will be extracted at index visit and all visits in the follow-up period (coded as controlled vs. not).
- Generalized linear mixed models (GLMM) with time nested within patients will be used to determine if risk factor control differs across encounter types, to estimate the effect of encounter type on change over time in CVD risk score and BP and A1c control. All encounters for each eligible patient will be included. CVD risk is influenced by factors amenable to clinical intervention (e.g., BP) and others that are irreversible (age); absent intervention, overall risk should increase with age. These analyses will be adjusted for or stratified by potential confounders at the patient, provider, and encounter level. This will include accounting for whether post-index visit encounters were in-person or VC, and the reason for the encounter, as in-person encounters in the post-COVID period may be for different reasons than VC encounters.

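### The supplement leaves open using a hypertension diagnosis code as a proxy for an updated blood pressure in a primary outcome, which could bias the in-person versus virtual comparison

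*Combined protocol and SAP*

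**What the plan says.** Aim 2 of the supplement is to "Compare CVD risk management in high-risk patients at in-person vs. virtual care (VC) encounters" (Section 2, Specific Aims). Section 3 defines virtual care as video or telephone encounters.

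The Supplement Addendum table in Section 6.b (Data Collection) lists, as the first primary outcome, "patients with up-to-date BP documented in EHR by 6 months" after the index visit, by encounter type, with a parallel item for A1c. Two notes follow. The first says "These outcomes will be adjusted for # of encounters in follow-up" period, and adds a provision about A1c monitoring. The second concerns blood pressure only: "We will consider using coding of a hypertension diagnosis at index" and, continuing the same sentence, "and follow-up encounters as a proxy for updated BP".

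The table does not say when the proxy would apply, whether it would fill gaps or replace recorded values, or whether results without it would be shown. Section 7.a (Supplement Addendum, Regression Analyses) restates the outcome as documentation of BP and A1c, "accounting for whether BP data were taken in person or reported by the patient". It does not mention the proxy.

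**The concern.** The outcome asks whether a blood pressure was recorded. A hypertension code shows that the diagnosis was noted or billed at a visit. It contains no reading and can be entered at a telephone encounter where none was obtained. Letting the code stand in for a reading swaps one event for another.

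In this comparison the missing reading is the signal. The supplement exists to learn whether the move to virtual care weakened risk-factor monitoring, and a virtual visit without a blood pressure is how that would show. If virtual care leaves more patients without a reading, a gap-filling proxy has more to fill in there. The likely consequence is an estimate that makes virtual care look closer to in-person care than it is.

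The timing adds a second difficulty, because the note refers to coding at index as well as at follow-up. If an index code alone were enough, a code entered on day 0 could credit an update that was due over the next six months. If codes at both were required, fewer patients would be credited. The text does not settle which is meant.

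**Working it through.** **The plan's own figure.** The only power statement for the supplement (Section 7.a, Statistical Power) concerns CVD risk score: 6000 per group, difference in mean change 5.0, SD 9.1 at each time point, correlation 0.200, two-sided alpha 0.05.

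SD of change = √(9.1² + 9.1² − 2 × 0.2 × 9.1 × 9.1) = √132.496 = 11.51. Power computes to 1.000, so the stated 100% reproduces. It has no bearing on blood pressure documentation, for which the documents give no rates and no power.

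**Inputs for the proxy (all assumed).** True share with a recorded blood pressure: p₁ = 0.90 in person, p₂ = 0.60 virtual. Share of patients without a reading who are credited through the code: q₁ and q₂. The proxy is taken to fill gaps: a patient counts as up to date if there is a reading or a code.

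**Formula.** Observed rate = p + (1 − p)q. With q₁ = q₂ = q, observed gap = (p₁ − p₂)(1 − q).

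| q (equal) | In person | Virtual | Gap (points) | Odds ratio |
|---|---|---|---|---|
| 0 | 90% | 60% | 30 | 6.00 |
| 0.2 | 92% | 68% | 24 | 5.41 |
| 0.5 | 95% | 80% | 15 | 4.75 |
| 0.7 | 97% | 88% | 9 | 4.41 |
| 0.9 | 99% | 96% | 3 | 4.13 |

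The risk difference reaches zero only at q = 1. The odds ratio shrinks less, because the ratio of not-up-to-date shares stays at 0.40/0.10 = 4 for any equal q below 1.

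**Unequal q.** Observed gap = 0.30 + 0.10q₁ − 0.40q₂.
- It is zero when q₂ = 1 − 0.10(1 − q₁)/0.40. At q₁ = 0.4 this gives q₂ = 1 − 0.06/0.40 = 0.85.
- Above that it reverses. At q₁ = 0.4 and q₂ = 0.95 the rates are 94% and 98%, a gap of −4 points.
- It widens when q₂ < q₁/4. At q₁ = 0.9 and q₂ = 0.1 the rates are 99% and 64%, a gap of 35 points.

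**Bias or power.** Take 6000 per group for illustration and ignore clustering. At q = 0.9 the standard error of the 3-point gap is √[(0.99 × 0.01 + 0.96 × 0.04)/6000] = √(0.0483/6000) = 0.0028, so z ≈ 0.03/0.0028 ≈ 10.6. The difference would still be detected easily. The problem is a precise estimate of the wrong size, not lost power.

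**Whether other text cures it.** Accounting for where a reading came from does not help, because a code carries no reading and is neither taken in person nor reported by the patient. Adjusting for the number of encounters, or for whether later encounters were in person or virtual, does not undo misclassification of the outcome itself.

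**The case against.** The strongest reply is that the plan commits to nothing here. The team will only consider the proxy, the outcome is defined as a documented blood pressure, and the regression section works from blood pressure data without mentioning a code. That is right: this is an open option, not an adopted analysis. It still needs closing, because the option is attached to a primary outcome and has no rule for its use.

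A reader might infer that the proxy would erase the in-person versus virtual contrast. The documents do not support that. With equal filling the gap shrinks by the factor (1 − q) and vanishes only if every patient without a reading carries a code. Eligibility (Section 5.b) runs through reversible risk, diabetes or existing ASCVD and does not require hypertension, so some patients would never be credited. Low values of q are plausible, and at 0.2 most of the gap survives.

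A reader might also infer that the bias must run toward no difference. That follows if the code fills gaps at similar rates in both groups. Unequal rates can reverse or widen the gap, and if the code replaced blood pressure for everyone the formula does not apply and the direction is unknown.

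It is also fair to say that recorded values have their own error. The documents do not establish that every patient-reported reading at a virtual visit reaches the EHR as a dated value. This is a reason to keep the code available for a sensitivity analysis. It does not make a code equivalent to a reading.

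**Conclusion.** The point holds as a conditional one. If the proxy enters the primary definition, virtual encounters with no reading could be counted as up to date, and the comparison the supplement is built on would be biased. Under equal gap-filling the loss runs from 6 of 30 points (q = 0.2) to 27 of 30 (q = 0.9). Those sizes rest on assumed documentation and coding rates and on the proxy filling gaps rather than replacing readings; none of this is in the documents.

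The scope is limited. The A1c half of the outcome, the needed-care outcome and the change-in-risk outcomes are not defined through the code, and the randomized Aim 1 comparison is untouched. The correction should nonetheless be made before the supplement is analysed, because the measure is unsuited to the outcome whether or not the choice is specified in advance.

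**What to change.** In the Section 6.b table, define the primary outcome as a dated blood pressure value recorded in the EHR within six months after the index visit, flagged as taken in person or patient-reported, the distinction Section 7.a already plans to use. Delete the diagnosis-code note from the primary definition. If the team wants the code, confine it to a sensitivity analysis labelled as such. State there whether a code at index, at follow-up or at both is required and whether it fills gaps or replaces readings, and report the share of patients credited by code alone in each encounter group.

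This changes one line and needs no new data. The costs are a lower up-to-date rate than the proxy would give, and the loss of patient-reported readings not stored as dated values. If such readings are missed more often at virtual visits, the in-person versus virtual gap could be overstated, so that limitation should be stated alongside the result.

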	# in-person / VC encounters between index visit and end of follow-up
	# in-person / VC encounters between index visit and end of follow-up period; was the encounter with the PCP: YN; visit's primary purpose;
encounters	# in-person / VC encounters between index visit and end of follow-up period; was the encounter with the PCP: YN; visit's primary purpose; whether visit was for an urgent need: YN; patient new vs. established
encounters  Provider factors	# in-person / VC encounters between index visit and end of follow-up period; was the encounter with the PCP: YN; visit's primary purpose; whether visit was for an urgent need: YN; patient new vs. established Degree (MD, RN, PA, etc.); Prescribing privileges: YN; # in patient panel
Provider factors Independent vars.	# in-person / VC encounters between index visit and end of follow-up period; was the encounter with the PCP: YN; visit's primary purpose; whether visit was for an urgent need: YN; patient new vs. established Degree (MD, RN, PA, etc.); Prescribing privileges: YN; # in patient panel Description

#### (2) Selected Clinics

- We will conduct semi-structured phone interviews with care team members involved with implementing/using CV Wizard, about 10 months postimplementation. Follow-up interviews will be conducted as needed, to explore perceptions, acceptance, and use of CV Wizard and the implementation support provided. Sites will be purposively sampled for diversity in CV Wizard use rates.
- We will administer a provider survey that asks about use of the tool and solicits feedback. The survey will be programmed in REDCap and sent to clinic contacts via email. The clinic contact will be asked to email the providers at their clinics directly to request survey completion. Providers are informed (via the consent language that accompanies the survey) that (1) all responses/results are anonymous, and (2) we will aggregate non-identifiable response data to provide feedback to their clinic's study champion. NOTE: This survey may be administered to some clinics more than once over the course of the study period.

## (3) Case Study/Supplement Clinics

- For case study sites, we will perform an in-depth ethnographic case study, which
  may include observation/personal interaction to explore the dynamics underlying
  implementation outcomes. We will follow the Arm 1 case study clinics for 2.5 years,
  the Arm 2 case study clinics for 1.5 years. Methods may include naturalistic
  observation (of workflows, patient encounters, clinic meetings), key informant and
  in-depth interviews, and collecting relevant artifacts (process maps,
  communications, etc.).
- For supplement sites, we will perform interviews with CHC staff and patients.

Interviews will occur ≥3 months after CV Wizard is activated at a given clinic, and we will follow these clinics for one year.

## 7. Data Analysis

### a. Analysis Plan

#### Overview

In this service area pragmatic clinical trial, we will implement CV Wizard via a staggered process. We will compare patients' CVD outcomes in the Arm 1 vs. Arm 2 CHCs, in months 18-35 (Aim 1); assess whether the revised implementation support materials expedite CDS adoption (Aim 2); and use mixed methods to identify multi-level barriers/facilitators to adoption of the CDS tool (Aim 3).

#### **Quantitative Data**

To be included in Aim 1 analyses a patient must have at least one visit in the 6 months after the Arm 1 implementation date at an Arm 1 or Arm 2 CHC and at least one additional visit at a study clinic in the 12-month post-index visit period. The first visit is referred to as the index visit. We will describe those who had inadequate follow-up data (did not have at least one additional visit in the post-index period). For each study subject, CVD risk score / risk factor management status will be calculated at index visit and each encounter during follow-up. While the tool can be run for patients of any age, we will restrict our analyses to patients 40-75 years of age.

We will test for between-group differences in baseline characteristics such as age, sex, race and ethnicity, insurance type, visit count, and health status using chi-square, t-test, and nonparametric Wilcoxon rank-sum tests as appropriate. We will also test for association between baseline characteristics and our outcomes of interest. We will examine the number of patients seen in each service area and clinic and each Arm and compare the characteristics of Arm 1 patients for whom the tool was used to those in Arm 1 for whom the tool was not used and to Arm 2 patients. Because the two arms were selected based on clinic size, percent of patients with a diagnosis for hypertension and the percent of patients that use tobacco, we anticipate there will be differences between the two groups resulting in the need to adjust for these differences. We will also examine characteristics at the service area and clinic-level in Arm 1 for whom the tool was used compared to Arm 1 service areas / clinics for whom the tool was not used and Arm 2 service areas / clinics.

Unadjusted trends in the monthly use and view rates for each of the study CHCs will be explored with use rates defined as: the number of encounters where CV Wizard was printed / number of targeted encounters with high-CVD risk patients per month and view rates defined as the number of encounters where CV Wizard was viewed / number of targeted encounters with high-CV risk patients per month.

We will also examine overall rates of each of the impact outcomes (BMI in normal range, controlled blood pressure, controlled LDL, controlled HbA1c, and non-smoking status) pre/post tool use to assess any changes in patterns for patients in Arm 1 for whom the tool was used compared to those in Arm 1 for whom the tool was not used as well as to Arm 2 patients. The date the tool was first used for each patient will be assigned as the start of the post-period.

Extent of adoption of a CDS tool like CV Wizard directly impacts its population-level impact. To differentiate between the tool's population level impact versus impact when used, we will conduct intent to treat (ITT) analyses to compare all targeted patients at intervention versus control clinics. We will also conduct effect of treatment on the treated (ETOT; also called per protocol) analyses limited to intervention CHC patients for whom the CV Wizard tool was used (results viewed / printed out) at the index visit, compared to intervention clinic patients for whom it was not used, and separately, to control clinic patients. The ITT analyses test the hypotheses that targeted patients in intervention clinics will have significantly lower CVD risk scores and higher rates of CVD risk factor control, at visits in the year post-index visit period, compared to similar patients in control clinics. The ETOT analyses test the hypotheses that targeted patients in intervention clinics for whom the CV Wizard CDS tool results are viewed and / or printed will have significantly lower CVD risk scores and higher rates of CVD risk factor control, at visits in the year post-index visit period, compared to similar patients in control clinics, and compared to patients in intervention clinics for whom the tool alerted but was ignored at the index visit.

Analyses will be stratified by first-time and repeat patients to see if there is a difference in tool use as well as examine whether the time between visits effects tool use among repeat patients.

